#### **Inclusion criteria**

1. Outpatients of either gender, age  $> 18$
2. Willing and able to give informed consent and adhere to visit/protocol schedules. (Consent must be given before any study procedures are performed)
3. Women of childbearing potential must have a negative urine pregnancy test. This will be confirmed before participation in this investigational protocol.
4. Either have a diagnosis of PAH, isolated left heart disease or lung disease (chronic obstructive pulmonary disease or interstitial lung disease) or CTEPH using established clinical criteria.
5. Patients undergoing right heart catheterization for evaluation of PAH or other cardiac or pulmonary disease for MRI scans

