  - 3.2.1 The primary focus of Aim 3 is to compare Xe MRI capability to detect absence/presence of pre/post-capillary PH to the gold standard of RHC
    - a. For this PFTs are not necessary, so they are ancillary
    - b. However, they are a standard way to characterize patients for publications, etc, so we would like to get them if we can. Getting them from the medical record is perfectly adequate for this purpose.
      - i. If PFTs are not available from the medical record, they are not so critical as to prevent us from enrolling the subject. In publications we will simply acknowledge the realities of COVID for this missing data.

This will be a single-blinded, open-label study enrolling volunteers and patients with pure PAH (10 subjects), pure left heart disease (10 subjects), pure lung disease (10 subjects) and CTEPH (5 subjects) [Aim 1] followed by a larger cohort of 92 subjects who are undergoing right heart catheterization for evaluation of PAH or other cardiac or pulmonary disease. [Aim 2]. We plan to consent 127 subjects. No subject will be excluded from the study on the basis of gender or ethnicity. Female subjects of childbearing potential will undergo urine pregnancy testing before each MRI. The urine pregnancy test must be negative to continue participating in the study. To refine the precision of Xe MRI for imaging gas transfer efficiency,

we will acquire a hemoglobin level by finger sensor device for each subject testing at each study visit. Informed consent will be obtained before a subject begins any study intervention. Subjects will undergo an approximately hour long comprehensive MRI protocol

Patients with PAH, CTEPH, left heart disease and lung disease will be recruited using minimally restrictive inclusion/exclusion criteria. The Duke Center for Pulmonary Vascular Disease sees approximately 150 patients for evaluation of PAH including CTEPH in a year. For the first phase of the study, whether patients are receiving approved therapies, enrolled in clinical trials, or receiving no therapy, all will be eligible for inclusion in this MRI study. For the second phase of the study, patients who have PAH and receiving approved therapies, patients who are being evaluated for PVD or other cardiac or pulmonary disease will be included in the study.

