## 5. Selection of Subjects:

We propose to recruit and consent 10 subjects with known PAH, 10 subjects with isolated left heart disease, 10 subjects with isolated lung disease (either chronic obstructive pulmonary disease or interstitial lung disease) and 5 patients with CTEPH, followed by 92 subjects undergoing or having undergone an evaluation for PAH over the course of this research. These subjects will undergo an approximately hour long comprehensive MRI protocol, including hyperpolarized Xe administration. No subject will be excluded from the study on the basis of gender or ethnicity. Female subjects of childbearing potential will undergo pregnancy testing at study entry, and before each procedure. Informed consent will be obtained before a subject begins any study.

**Definition of PAH:** Mean PA pressure  $\geq$  25 mmHg with PCWP  $\leq$  15 mmHg and PVR  $\geq$  3 WU in the absence of significant left heart disease, lung disease, chronic pulmonary embolism, hemolytic anemia, sarcoidosis and cancer.

**Definition of isolated left heart disease:** Any of the following:

- 1) A mean PA pressure  $\geq$  25 mmHg with PCWP  $>$  15 mmHg and PVR  $<$  3 Woods units at right heart catheterization.
- 2) LVEF  $=<$  40% with mild or less RV enlargement and dysfunction on echocardiogram.

Evidence of diastolic dysfunction (as assessed by expert reader) with mild or less RV enlargement and dysfunction on echocardiogram.

**Definition of isolated lung disease:** A mean PA pressure  $<$  25 mmHg at right heart Cath AND/OR an estimated right ventricular systolic pressure of  $<$  40 on echocardiography AND/OR no diagnosis of heart

failure or pulmonary hypertension IN THE SETTING OF obstruction (FEV1/FVC < 0.7) on pulmonary function testing AND/OR radiographic evidence of lung disease.

**Definition of CTEPH:** Subjects with a history of a mean PA pressure  $\geq 25$  with evidence of chronic thromboembolic disease on imaging studies. Images may be obtained before and/or after pulmonary thrombendarterectomy (PTE) surgery for removal of blood clots from the lungs.

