#### **6. Subject Recruitment & Compensation:**

Patients will be recruited based on predetermined inclusion/exclusion criteria. They will be recruited in the pulmonary and cardiology clinics and inpatient services at Duke by their providers. The patient's provider will initiate conversation with the subject about the research trial and assess their interest in participation. The screening of subjects will be conducted by the study coordinator and will include the informed consent process.

Before entry into the protocol, the nature and risks of the study will be reviewed with each subject. Each subject will be given the opportunity to read the consent form and ask questions. After all questions by the study subject are answered, and before any protocol specified procedures are initiated, each subject will sign and date the consent form. A copy of the signed consent will be provided to the subject.

After informed consent is obtained, potential subjects will be screened to determine if they satisfy all inclusion and exclusion criteria. If subjects agree to participate, they will be consented into the study by the clinical coordinator in a private room. All potential subjects will be given a description of the procedures, have the opportunity to read the consent form, and to ask any questions. All subjects are free to decide whether or not to participate. It will be made clear to all subjects that their decision to participate or decline, will in no way affect their medical care. For all subjects, informed consent will be documented by having the patient sign a standard research consent form approved by the Duke IRB.

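### The inclusion list must be met in full, yet criteria 4 and 5 describe two different cohorts; read literally, it bars intended subjects from both

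*Combined protocol and SAP*

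**What the plan says.** The Inclusion criteria in Section 5 form one numbered list of five, with no cohort headings.

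- Criterion 1 begins "Outpatients of either gender, age" and so admits outpatients only.
- Criteria 2 and 3 cover consent and pregnancy testing and fit every cohort.
- Criterion 4 reads "Either have a diagnosis of PAH, isolated left heart disease or lung disease (chronic obstructive pulmonary disease or interstitial lung disease) or CTEPH", to be judged by established clinical criteria.
- Criterion 5 reads "Patients undergoing right heart catheterization for evaluation of PAH or other cardiac or pulmonary disease for MRI scans".

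Section 6 gives the joining rule: "potential subjects will be screened to determine if they satisfy all inclusion and exclusion criteria". The same section describes where patients are found: "They will be recruited in the pulmonary and cardiology clinics and inpatient services at Duke by their providers".

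The cohorts are described elsewhere. Section 4 sets out Aim 1 (10 PAH, 10 left heart disease, 10 lung disease, 5 CTEPH) and then 92 patients having RHC. For the second phase it names PAH patients on approved therapy, and adds that "patients who are being evaluated for PVD or other cardiac or pulmonary disease will be included in the study". Section 5 describes the second group slightly differently: "followed by 92 subjects undergoing or having undergone an evaluation for PAH over the course of this research".

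**The concern.** Criterion 4 is a ticket for Aim 1 and criterion 5 a ticket for the validation cohort, but the plan asks every subject to hold both. Screening staff then have two options. They can apply the list as written and turn away people the design means to enrol, or they can enrol those people and carry subjects who do not meet the written criteria.

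The first option has a statistical cost. The AUC tested in Section 12 is a property of the patients in whom it is estimated. A validation set that requires an existing diagnosis is weighted toward patients whose disease is already labelled. Such cases are usually easier to separate, so upward bias is the more likely direction, although the documents cannot settle either direction or size.

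The outpatient wording of criterion 1 against recruitment on inpatient services is a second, softer conflict in the same list.

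**Working it through.** **The plan's own figures.** Cohorts: 10 + 10 + 10 + 5 = 35, and 35 + 92 = 127, the number to be consented in Section 4. Section 12 gives 46 normals and 46 with disease for AUC 0.72 against 0.85, one-sided 5%, 80% power, binormal variance. With equal groups, V(A) = 0.0099 · exp(−a²/2) · [(5a² + 8) + (a² + 8)] and a = 1.414 · z(A):

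- V(0.72) ≈ 0.1415 and V(0.85) ≈ 0.0977.
- n = (1.645 · √0.1415 + 0.842 · √0.0977)² / 0.13² ≈ 46.02 per group, with power 0.80 at 46.

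The 92 therefore reproduces, and the problem is not in the sample size.

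**Criteria 4 and 5 against the cohorts they must serve, all criteria required:**

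| Intended subject | Criterion 4 | Criterion 5 | Result |
|---|---|---|---|
| Aim 1, left heart disease defined by echocardiogram (Section 5), no RHC | met | not met | barred |
| Aim 1, lung disease defined by echocardiogram, lung function or imaging (Section 5), no RHC | met | not met | barred |
| Second phase, first RHC for suspected PAH, no other listed diagnosis | not met | met | barred |
| Second phase, RHC normal, no heart or lung diagnosis | not met | met | barred |
| Second phase, RHC, known COPD, ILD, isolated left heart disease, CTEPH or PAH | met | met | admitted |
| Second phase, treated PAH, RHC in the past only | met | unclear | unclear |

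The third row follows from the Section 5 definition of PAH. It needs mean PA pressure, wedge pressure and PVR, "in the absence of significant left heart disease, lung disease, chronic pulmonary embolism, hemolytic anemia, sarcoidosis and cancer". The pressures and resistance come from the catheterization itself, so someone arriving for a first RHC cannot yet meet criterion 4 through PAH. That person belongs to the group still being evaluated, which Section 4 includes.

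The last row follows from tense. Criterion 5 says undergoing, Section 5's cohort sentence also covers those who have already undergone evaluation, and Section 4 admits PAH patients already on therapy.

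**Effect on the analysis.** If barred patients are replaced by others who meet both criteria, the set still reaches 92 and nominal power is unchanged. What changes is case mix. The documents give no diagnosis mix for RHC referrals, so the size of the shift cannot be computed.

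**Setting.** Criterion 1 admits outpatients, while Section 6 recruits from inpatient services. Footnote 2 to the Study Visit Schedule allows MRI on a different day from screening, so a patient approached on a ward could be an outpatient when scanned. No passage says at which point status is judged.

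**The case against.** The best answer is that the intent is already visible. Sections 4 and 5 separate the 35 diagnosed subjects from the 92 having RHC, and Section 4 calls the criteria minimally restrictive. The Section 6 sentence is also loosely drafted: taken word for word, it would have subjects satisfy the exclusion criteria too. This stands as far as it goes, and it is why the point is a drafting defect. It does not remove the defect. The opening word of criterion 4 introduces the diagnoses listed within it and does not reach criterion 5, and an unlabelled inclusion list is ordinarily applied in full.

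Several stronger readings are tempting and are not supported:

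- A reader might infer that most of the validation cohort is barred. No document gives the share, and many RHC patients could meet both criteria.
- A reader might infer that all patients with borderline pressures, normal haemodynamics or mixed disease are lost. Many could enter criterion 4 through COPD, ILD or left heart disease, and it is not clear that the word isolated attaches to lung disease in that criterion.
- A reader might infer that Aim 3 is meant only for diagnostically uncertain patients. Item 3.2.1 in Section 4 states its focus as presence or absence of pre- or post-capillary PH against RHC, and treated PAH patients are expressly included.
- A reader might infer that every inpatient enrolled is a deviation. The separate screening visit leaves room for a later outpatient scan.
- Criterion 4's appeal to established clinical criteria beside the Section 5 cut-offs might suggest two rival definitions. It is more naturally read as pointing to Section 5, so this is a minor matter of naming one source.

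**Conclusion.** The concern holds as a contradiction between the written eligibility rule and the plan's own cohorts. As worded, the list excludes second-phase RHC patients with none of the listed diagnoses and Aim 1 left heart or lung disease subjects who qualify without RHC. The conflict over care setting, and that between current and past RHC, are real but smaller.

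The number of subjects affected cannot be stated from the documents, and the sample size calculation is untouched. The possible bias in the AUC is conditional: it arises only if the list is applied literally, so that already-diagnosed patients displace those still being evaluated. If staff follow the evident intent, the consequence is instead that subjects are enrolled who do not meet the criteria as written. Either outcome is avoidable, so the wording should be corrected.

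**What to change.** Make one amendment to the eligibility wording:

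1. Split the list by cohort. Aim 1: criteria 1-3 plus criterion 4, with the Section 5 definitions named as the diagnostic source. The 92-patient cohort: criteria 1-3 plus criterion 5, stating that no prior diagnosis is required.
2. Change the Section 6 sentence so that subjects must meet all inclusion criteria for their own cohort and none of the exclusion criteria.
3. Reconcile criterion 5, which covers only current RHC, with Section 5, which also covers completed evaluation, and with the treated PAH patients named in Section 4. Splitting the list without this step would leave those patients in doubt.
4. Reconcile criterion 1 with recruitment from inpatient services by stating whether outpatient status is judged at recruitment or at MRI.

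The cost is the amendment itself. No extra subjects, visits or procedures are needed, and the figures 92 and 127 do not change.

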#### **Exclusion criteria**

1. Medical or psychological conditions which, in the opinion of the investigator, might create undue risk to the subject or interfere with the subject's ability to comply with the protocol requirements
2. Conditions that will prohibit MRI scanning (metal in eye, claustrophobia, inability to lie supine)

#### **6. Subject Recruitment & Compensation:**

Patients will be recruited based on predetermined inclusion/exclusion criteria. They will be recruited in the pulmonary and cardiology clinics and inpatient services at Duke by their providers. The patient's provider will initiate conversation with the subject about the research trial and assess their interest in participation. The screening of subjects will be conducted by the study coordinator and will include the informed consent process.

Before entry into the protocol, the nature and risks of the study will be reviewed with each subject. Each subject will be given the opportunity to read the consent form and ask questions. After all questions by the study subject are answered, and before any protocol specified procedures are initiated, each subject will sign and date the consent form. A copy of the signed consent will be provided to the subject.

After informed consent is obtained, potential subjects will be screened to determine if they satisfy all inclusion and exclusion criteria. If subjects agree to participate, they will be consented into the study by the clinical coordinator in a private room. All potential subjects will be given a description of the procedures, have the opportunity to read the consent form, and to ask any questions. All subjects are free to decide whether or not to participate. It will be made clear to all subjects that their decision to participate or decline, will in no way affect their medical care. For all subjects, informed consent will be documented by having the patient sign a standard research consent form approved by the Duke IRB.

[name] is founder and chief technology officer of Polarean, Inc. a start-up company that seeks to commercialize hyperpolarized  $^{129}\text{Xe}$  gas MRI technology. He is a shareholder in the company and provides it with technical consulting. In addition, Polarean has licensed from Duke, a patent on which [name] is an inventor, and is currently evaluating several others. For these reasons he has had a conflict management plan, administered by the Duke Office of Research Integrity. The study proposed here uses Polarean technology, but is not sponsored by the company nor is it being used for regulatory advancement with FDA. However, if the findings are positive, Polarean may have an interest in commercializing these aspects of the technology as well. Therefore, consistent with his management plan, [name] will not serve as principal investigator on this study, nor will he obtain consent from subjects. He will oversee the technical aspects of hyperpolarized gas production and MR image acquisition. However, data analysis will be overseen by [name], who also serves as overall principal investigator on this protocol.

#### **7. Consent Process:** see Section 14 of the e-IRB submission form.

**8. Subject's Capacity to Give Legally Effective Consent:** Subjects without capacity to give consent will not be recruited into this study.

**9. Study Interventions:**

Hyperpolarized xenon will be administered in multiple doses in volumes up to 25% of subject TLC followed by a breath hold of up to 15 seconds. Subsequent Xe doses will only be administered once the subject is ready to proceed. Hyperpolarized Xe MRI will be used to acquire one or all of the following data:

1. Xe calibration dose to test coil tuning and loading in each subject to permit optimal setting of imaging parameters.
2. Xe distribution after inhalation and breath-hold as an indicator of regional pulmonary ventilation.
3. Xe signal dissolved in the pulmonary interstitial spaces and capillary blood as an indicator of pulmonary gas exchange.
4. Xe spectroscopy to follow the dynamics of gaseous and dissolved-phase Xe.
5. Any of these Xe exams may be repeated if deemed necessary by the study team.
6. Conventional H MRI will be used to provide anatomical reference scans, as well as pulmonary perfusion. These will include some or all of the following:
  7. 3-Plane Localizer
  8. A variety of breath-hold 3D H MRI scans to delineate the thoracic cavity
  9. Free-breathing UTE H MRI to image tissue density and edema

**Study Visit Schedule**

Protocol Activities	Screening (V0)	Study Visit (V1)	Study Visit (  V2) only for CTEPH subjects)	Follow Up/Release (after last dose)	Follow-up contact w/in 24 hr
Informed Consent	X				
History re: Disease	X				
Medical History	X				
Pregnancy Test 	(X)	(X)	(X)		
MRI Screening  Form	X	(X)	X		
Imaging Session  .		X	X		
Pulmonary Function Testing 	(X)	(X)			
Adverse Events 		X		X	X
Vital Signs Assessment with optional non-invasive, optical Hemoglobin measurement	X	X	X	X	

 for women of child bearing potential, a urine pregnancy test will be performed on the day of the MR examination. The test must be negative before MRI. The pregnancy test will be conducted and interpreted by study personnel who have completed competency training from the Duke Office of Clinical Research (DOCR).

 An MRI screening form will be completed at the screening session and will be verified prior to starting the imaging session. If a MRI is performed on a different day from the screening session, subject will need to complete a new MRI screen form.

The MRI session will be conducted on the CAMRD research MRI scanner. Hyperpolarized Xe is produced and delivered by the study team. Macroyclic contrast agents are available at the scanner. During the 1-hr MRI session, a qualified medical professional (MD, DO, PA, LNP, RN, RT or MT) will be on hand to monitor subjects during MRI and note any symptoms related to xenon MRI or contrast administration.

PFTs may not be acquired if subjects are undergoing scans for technical development purposes only or have such data available in their medical record.

Based on the known pharmacokinetics of xenon, no additional effects are expected after subject is released from the imaging study. However, subjects will be contacted 24 hours after their participation to enable them to report any additional effects or events.

Subjects will CTEPH will be asked to return for a second MRI. The second MRI will be done post-surgically.

## 10. Risk/Benefit Assessment:

### Potential Risks

The risks of participating in this study are considered greater than minimal risk. MRI is a non-invasive imaging modality that involves no ionizing radiation. All subjects will have already completed a standard questionnaire to screen for contraindications to MRI imaging since the parent trial also employs MR imaging.

### Risks of Xenon Inhalation

Inhalation of hyperpolarized Xe may carry some minor risks. Xenon is a general anesthetic when breathed continuously at concentrations greater than 70% for extended periods of time. In the proposed study, xenon will be delivered in a single breath, with alveolar concentrations below 25%. At these concentrations, subjects may experience transient effects including dizziness, slight tingling or numbness of the extremities, nausea, smelling of flowers, or a feeling of well-being and euphoria. These effects will wane within 1-2 minutes of exhaling the xenon and are documented in the consent forms.

A second risk comes from administering HP Xe without oxygen. This is necessary to preserve good image quality, because O2 is paramagnetic and depolarizes the HP Xe. Administration of a single anoxic 1-liter breath has been well tolerated by subjects undergoing both He and Xe MRI because for a single breath, the residual oxygen in the subject's lungs is sufficient to maintain blood O2 saturation during the breath-hold. Numerous studies have now been published demonstrating the safety and tolerability of hyperpolarized Xe MRI.

Hyperpolarized Xe is treated as a drug by the FDA and is covered by our existing Investigational New Drug Filing (IND# 109,490), which has been active for 7 years and has reported no SAEs, and no early withdrawals from the study. The proposed studies will use hyperpolarized Xe prepared in exact accordance with the Drug Master File that is part of the IND held by Polarean, Inc. Our center has been granted the rights by Polarean to cross-reference this IND for their own filings. We will continue to follow a Xe administration protocol that is well established in our hands.

